# 1.1.2.6 Phase II Clinical Study in Patients with Lumbar Disc Herniation (Study Number: 6603/1121) (USA)

This study was an open-label, multicenter, sequential dose-escalation study. The objective of this study was to evaluate the safety of SI-6603 in lumbar disc herniation patients (L4–L5 or L5–S1) followed for 52 weeks after administration of SI-6603 into an intervertebral disc. Exploratory efficacy endpoints were investigated. Patients received a single 1.0 mL injection of SI-6603 (0.5 U, 1.25 U, or 2.0 U) into the nucleus pulposus of an intervertebral disc of each patient. A Data Safety Monitoring Board (DSMB) evaluated safety and tolerability once the Week 13 data were available for each cohort. On the basis of the recommendation of the DSMB, the Sponsor proceeded to the next higher dose for the second (1.25 U) and third cohorts (2.0 U).

A total of 17 patients (94.4%) in the safety population experienced 39 AEs. Two patients (11.1%) discontinued the study due to an AE and no patient discontinued due to a treatment-related AE. No patient experienced a SAE or died during the study.

The most frequently observed treatment-related AE with an incidence of  $\geq$ 3 patients in the total safety population was nuclear MRI abnormal (4 patients, 22.2%). The event was all mild in intensity and did not require intervention in all patients. The following 3 treatment-related AEs (each reported for a different patient) were not resolved before the end of the study: nuclear MRI abnormal, spinal X-ray abnormal, and dysesthesia.

Seikagaku Corporation	Clinical Study Protocol
Protocol Number 6603/1132	CONFIDENTIAL

Clinical observations of the patients with these treatment-related AEs were terminated after each patient's condition was determined to be stable.

Evaluation of translation and angulation of vertebral bodies did not raise safety concerns. One patient had a decrease in disc height  $\geq$ 30%. Overall, 6 patients (33.3%) in the safety population had a change to Modic classification Type I or II, which included 1 patient (20.0%) in the 0.5 U dose group, 3 patients (50.0%) in the 1.25 U dose group, and 2 patients (33.3%) in the 2.0 U dose group.

No patient had an increase in serum anti-SI-6603 IgE antibody titer. At Week 13, one patient each from the 0.5 U, 1.25 U and 2.0 U dose groups had an IgG antibody titer that was increased by one grade from baseline, but with unclear SI-6603 specificity.

Efficacy evaluations showed improvement from baseline in leg pain Visual Analog Scale (VAS). At Week 13, the mean worst leg pain values that were assessed during the 7 days prior to the Week 13 visit were 9.1 mm in the 0.5 U dose group, 38.4 mm in the 1.25 U dose group, and 5.1 mm in the 2.0 U dose group. Improvement of the worst leg pain in the treatment groups also continued beyond Week 13. At screening (baseline), the values were 65.9 mm in the 0.5 U, 70.8mm in the 1.25 U, and 81.7mm in the 2.0 U, at the final observation at Week 52 the values were 24.0 mm in the 0.5 U dose group, 39.0 mm in the 1.25 U dose group, and 13.2 mm in the 2.0 U dose group. Mean worst back pain values at Week 52 that were assessed during the 7 days prior to Week 52 visit were lowest in the 2.0 U dose group (11 mm) and highest in the 1.25 U dose group (45 mm).

The plasma SI-6603 concentration was below the limit of quantification in all patients at all time points (<100  $\mu$ U/mL).

In conclusion, SI-6603 was well tolerated for up to 52 weeks after administration with no major safety concerns. SI-6603 improved leg pain and underlying symptoms of lumbar disc herniation.

#### 1.1.2.7 Phase III Clinical Study in Patients with Lumbar Disc Herniation (Study Number: 6603/1031) (Japan)

This study was a multicenter, randomized, double-blind, placebo-controlled, comparative study that sought to verify the superiority of SI-6603 versus a placebo at 13 weeks after single-dose administration of 1.25 U of SI-6603 or the placebo into the nucleus pulposus of an intervertebral disc of patients with lumbar disc herniation (L4–L5 or L5–S1). A further objective of this study was to monitor the stability of the intervertebral disc and surrounding tissue up to 52 weeks after administration.

The LSM of the primary endpoint of change from baseline in worst leg pain over the past 24 hours at Week 13 was –34.3 mm in the placebo group and –49.5 mm in the 1.25 U group showing significant difference for the 1.25 U group compared to the placebo group.

Seikagaku Corporation	Clinical Study Protocol
Protocol Number 6603/1132	CONFIDENTIAL

The LSM change from baseline in worst leg pain at the final observation in Week 52 was -42.3 mm in placebo group and -54.2 mm in 1.25 U group; showing significant difference for SI-6603 group compared to the placebo group.

In the safety evaluation, SAEs were seen in 10 of the 163 patients treated with the investigational drugs (placebo group: 6 patients and 1.25 U group: 4 patients). In 10 patients with SAEs, a causal relationship with the investigational drug could not be ruled out for 1 patient in the 1.25 U group with back pain. Five patients in the placebo group discontinued the study due to an AE but no causal relationship with investigational drug was established for any of these events. Severe AEs occurred in 13 of the 163 patients treated with the investigational drug (placebo group: 7 patients and 1.25 U group: 6 patients). A causal relationship with the investigational drug could not be ruled out for 1 patient in the 1.25 U group with toxic skin eruption.

The incidence of treatment-related AEs was 33.3% in the placebo group and 57.3% in the 1.25 U group, with a significant difference between the 1.25 U group and the placebo group.

In the 1.25 U group, treatment-related AEs with a high incidence were back pain (placebo group: 4.9%; 1.25 U group: 24.4%), nuclear MRI abnormal (placebo group: 12.3%; SI-6603 group: 24.4%), and spinal X-ray abnormal (placebo group: 3.7%; SI-6603 group: 23.2%). Treatment-related AEs in the 1.25 U group with an incidence that is higher by10% or more than placebo were back pain, nuclear MRI abnormal, and spinal X-ray abnormal. The severity of all treatment-related AEs with high incidence was mild or moderate. Patients in the 1.25 U group with AEs relating to the stability of the intervertebral disc (decrease in disc height of  $\geq$ 30% and intervertebral posterior angle of  $\geq$ 5°) showed a trend towards a high incidence of the treatment-related AE of low back pain.

No patients were found to have an elevated serum anti-SI-6603 IgE antibody titer. One patient each from the placebo group and the 1.25 U group exhibited an elevated serum anti-SI-6603 IgG antibody titer but neither experienced any AEs characterized by allergy-like symptoms.

# 1.1.3 Additional Information

Further details can be found in the current Investigator's Brochure (IB), which contains comprehensive information on SI-6603.

# 1.1.4 Current Study

The current study is a Phase III, multicenter, open-label, study of SI-6603 in patients with lumbar disc herniation. Patients will receive a single intradiscal dose of SI-6603 1.25 U injection. Safety and efficacy will be followed for 26 weeks after investigational drug administration. See Section 3.1 for details concerning the design of the current study and Section 3.3 for study design justification of this study.

#### 1.2 Rationale

#### 1.2.1 Study Rationale

Lumbar disc herniation is treated primarily with conservative non-operative therapy. However, in patients who fail to respond to this therapy, surgery is one of the only remaining options. The target population of this study is patients with signs and symptoms of lumbar disc herniation who failed conservative therapy and who have not received surgery at the target level or who qualify for surgery but wish to avoid it. Patients who require immediate surgical intervention such as those with significant neurologic deficit will be excluded.

The results of the Japanese Phase II/III clinical study (Study Number: 6603/1021) suggest that SI-6603 intradiscal injection is safe and effective in improving the signs and symptoms of lumbar disc herniation. In addition, the Japanese Phase III clinical study (Study Number: 6603/1031) verified that SI-6603 intradiscal injection is safe and effective in improving the signs and symptoms of lumbar disc herniation. Therefore, conducting a further clinical study intended to assess safety and efficacy of intradiscal SI-6603 at a dose of 1.25 U was proposed.

#### 1.2.2 Rationale for Dose and Schedule Selection

The intradiscal route was selected as the route of SI-6603 administration for this study. SI-6603 acts by decreasing intradiscal pressure and ameliorating pressure on the spinal nerve root by decomposing glycosaminoglycan chains (e.g., chondroitin sulfate) of proteoglycan present in the nucleus pulposus of an intervertebral disc. This reduced the water retention by the proteoglycan.

The dose selected for this study was 1.25 U administered as a single injection into the intervertebral disc, based on the result of the Japanese Phase II/III clinical study (Study Number: 6603/1021) and the Japanese Phase III clinical study (Study Number: 6603/1031), where the 1.25 U dose was shown to be safe and effective.

A retrospective follow-up prognostic study of patients with lumbar disc herniation was conducted 6 years after the Japanese Phase I/II clinical study (Study Number: SKK6603J01). There were no occurrences of lumbar surgery or worsening of the clinical symptoms (see Section 1.1.2.3).

Single-dose administration was selected for SI-6603 rather than repeat dose administration due to the risk of allergic reaction with multiple injections that is unlikely, but possible, to occur due to the heterologous protein preparation of *Proteus vulgaris*.

#### 1.3 Risk-Benefit Assessment

Lumbar disc herniation is treated primarily with conservative nonoperative therapy. However, in patients who fail to respond to this therapy, surgery is one of the only remaining options. This indicates an unmet medical need for a less invasive and safe

Seikagaku Corporation	Clinical Study Protocol
Protocol Number 6603/1132	CONFIDENTIAL

therapy that is effective in treating lumbar disc herniation in patients who fail to improve with nonoperative therapy.

The more common possible risks of injecting SI-6603 are back pain, nuclear MRI abnormal (Modic change), and spinal X-ray abnormal (decrease of disc height) Table 1. In past studies, the severity of back pain was mostly mild to moderate and symptoms recovered or resolved either without intervention or after appropriate treatment in most of the patients. Modic change and decrease of disc height were assessed as mild in severity in past studies and none of the affected patients exhibited any clinical symptoms posing safety concerns. Decrease of disc height in SI-6603 treated patients was assessed mild in severity in past studies and the degree of disc height decrease was considered comparable to or less than the lumbar discectomy.

In Japanese Phase II/III and Phase III studies, administration of SI-6603 1.25 U/mL demonstrated clinically significant improvement of leg pain and favorable improvement of back pain in lumbar disc herniation patients with contained-type hernia (unruptured posterior longitudinal ligament) who failed to improve after undergoing conservative treatment for a period of more than 6 weeks.

Taken together, it is considered that the risks of SI-6603 are manageable and the potential benefits outweigh those risks. During the study, X-ray and MRI assessments will be conducted to investigate the possibility of abnormalities. If any abnormalities occur, patients will be able to obtain immediate proper treatment. Detailed assessment of anticipated possible risks and benefits are stated below.

# 1.3.1 Possible Risks

#### 1.3.1.1 Treatment-related Adverse Event

Information on major AEs and treatment-related AEs that were observed in SI-6603 clinical studies in patients with lumbar disc herniation are summarized below. The follow-up periods in the previous clinical studies were up to one year after the administration of a single-dose of SI-6603 into the intervertebral disc (Table 1).

 The SAEs for which a causal relationship with SI-6603 could not be ruled out included: 4 events (pruritus, exanthema, skin warmth, and bullous dermatitis) in 1 patient in the 0.5 U dose group in the Japanese Phase I/II clinical study. All events were moderate in severity. However, they were processed as SAEs because of prolongation of an existing hospitalization.

1 event (back pain) in 1 patient in the 1.25 U dose group in the Japanese Phase III clinical study. Although the event was moderate in severity, it was processed as SAE because inpatient hospitalization was required for nucleotomy.

2. The high incidence AEs for which a causal relationship with SI-6603 could not be ruled out:

Seikagaku Corporation	Clinical Study Protocol
Protocol Number 6603/1132	CONFIDENTIAL

back pain, nuclear MRI abnormal (change in bone marrow adjacent to vertebral endplates; Modic change), and spinal X-ray abnormal (30% decrease of disc height).

- 3. Severe AEs for which a causal relationship with SI-6603 could not be ruled out: 2 events (lymphadenitis and neutrophil count decreased) in 2 patients in the 2.5 U dose group in the Japanese Phase II/III study, 1 event (back pain) in 1 patient in the 2.0 U dose group in the USA Phase II study, and 1 event (toxic skin eruption) in 1 patient in the 1.25 U dose group in the Japanese Phase III study.
- 4. Abnormal laboratory values considered to be AEs for which a causal relationship with SI-6603 could not be ruled out: neutrophil count decreased, C-reactive protein increased, blood triglycerides increased, white blood cell count decreased, alanine aminotransferase (ALT) increased, aspartate aminotransferase (AST) increased, blood bilirubin increased, Lasegue's test positive, eosinophil count increased and platelet count decreased. Of these AEs, only neutrophil count decrease (1 patient in the 2.5 U dose group in the Japanese Phase II/III study) was determined to be severe.
- 5. In the non-clinical data of the SI-6603 long-term (3 months to 3 years) observation studies following a single-dose intradiscal administration, bulging of nucleus pulposus tissues into the bone marrow cavity of the vertebral body (Schmorl's nodes-like lesions) associated with degeneration of cartilaginous endplates was observed in dogs. However, similar findings were not observed in clinical studies in Sweden, Japan, and the USA, or in non-clinical studies using rabbits and cynomolgus monkeys.

A listing of the AEs that occurred in clinical studies to date in SI-6603 treatment groups (269 patients in total; 0.5 U, 1.25 U, 2.0 U, 2.5 U, 5 U, and 10 U dose groups) and placebo (128 patients) are shown in Table 1.

# 1.3.1.2 Allergic Reactions

As SI-6603 is a foreign protein, it has the potential to cause anaphylaxis or severe allergic reactions. Anaphylaxis or severe allergic reactions were not observed in the Phase I/II, Phase II/III, and Phase III studies in Japan, and the Phase II study in the USA. In the Phase I/II study in Japan, 2 of the 18 patients exhibited AEs in the form of allergy-like symptoms for which a causal relationship with SI-6603 could not be ruled out. One of these patients developed a moderate case of pruritus, skin warm, exanthema, and dermatitis bullous, and the other patient developed a mild exanthema.

In the Phase II/III and Phase III studies in Japan, 6 of the 229 patients exhibited AEs in the form of allergy-like symptoms for which a causal relationship with SI-6603 could not be ruled out. One of these patients developed a severe toxic skin eruption.

All of these AEs in the form of allergy-like symptoms appeared 1 to 7 days after administration, but resolved after standard dermatological treatment.

No patients were found to have increased serum anti-SI-6603 IgE antibody titers.

#### 1.3.1.3 Back Pain

Treatment-related AEs of back pain were the highest reported incidence in past studies (64/269 patients). Severity was mostly mild to moderate with 2 severe events from the Phase III study in Japan and Phase II study in the USA, respectively.

Occurrence of back pain is likely to be influenced by the primary disease. However, back pain that occurred soon after administration of SI-6603 may be attributable to nucleus pulposus degradation. Thus, it is assumed that nucleus pulposus degradation by SI-6603 administration will accompany the spine's architecture and create dynamic changes that lead to the occurrence of temporary back pain. It is also assumed that a 1 mL intervertebral injection of SI-6603 may lead to an occurrence of back pain, which is caused by a temporary increase on intervertebral disc inner pressure.

#### 1.3.1.4 Decrease of Lumbar Disc Height and Change in Bone Marrow Adjacent to Vertebral Endplates

In past studies with SI-6603 administration, treatment-related AEs of nuclear MRI abnormal (change in bone marrow adjacent to vertebral endplates; Modic change) were reported in 22.3% (60/269 patients) and spinal X-ray abnormal were reported in 14.1% (38/269 patients). Among 38 patients reporting spinal X-ray abnormal, AEs included intervertebral posterior angle dilation (7 events) and 30 % decrease of disc height (34 events). However, none of the affected patients exhibited any clinical symptoms posing safety concerns. Furthermore, there was no leg pain or back pain accompanying the occurrence of instability of the intervertebral disc and surrounding tissues. The clinical significance of Modic changes remains unclear and past SI-6603 studies did not reveal any increase of leg pain or back pain in conjunction with Modic changes.

Spinal imaging changes following lumbar discectomy were reported by McGirt, et al. as 18%, 21%, and 26% decreases of disc height at 3 months, 6 months, and 2 years post surgery, respectively. In a follow-up study until 2 years after lumbar discectomy patients, Ohtori, et al. reported Modic changes in 7 (15.6%) of the 45 patients, with 1 of the 22 patients exhibiting a change from Modic Type 0 to Type 1, 3 of the 22 patients changing from Modic Type 0 to Type 2, and 3 of the 23 patients changing from Modic Type 0 to Type 2, and 3 of the 23 patients changing from Modic Type 1 to Type 2. In a Phase II/III study in Japan, percent decrease in disc heights was highest in the 5 U dose group at 17.4% at Week 13, 18.9% at Week 26, and 21.8% at Week 52. The reductions in disc height in the SI-6603 groups were equal to or milder than those of the above-mentioned lumbar discectomy patients. The incidence of treatment-related Modic changes was slightly higher in the SI-6603 groups than in the lumbar discectomy patients at 22.3%.

There is a possibility that changes in the bone marrow adjacent to vertebral endplates and decreases of lumbar disc height may occur as the result of SI-6603 administration in the

Seikagaku Corporation	Clinical Study Protocol
Protocol Number 6603/1132	CONFIDENTIAL

same degree as seen in lumbar discectomy. In addition, there is a possibility of vertebral body instability (intervertebral posterior angle and vertebral body translation).

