# 1.1.2.3 Prognostic Study of Patients with Lumbar Disc Herniation Administered with SI-6603 in Japanese Phase I/II Clinical Study (Japan)

A retrospective follow-up study was conducted 6 years after the initial study to confirm the long-term effects of SI-6603 on the degeneration of nucleus pulposus and vertebral stability of intradiscal administration.

Ten of the total 18 patients who participated in the initial Phase I/II clinical study consented to participate in this study. The observation period was 3.2 to 77.8 months after administration.

Seikagaku Corporation	Clinical Study Protocol
Protocol Number 6603/1132	CONFIDENTIAL

No patients had progressive disc height decrease, worsening of clinical symptoms, or lumbar surgery after the administration of SI-6603.

There were no clinically problematic events such as progressive decrease of disc height and worsening of clinical symptoms, and the findings were unchanged from the final observation time of the initial Phase I/II study (SKK6603J01). In patients who had changes in imaging findings, no clinical symptoms accompanied the changes. The results of this study supported the long-term safety of the disc and its surrounding tissue after administration of SI-6603.

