Treatment-related AEs with a high incidence in the SI-6603 groups were nuclear magnetic resonance imaging (MRI) abnormal, back pain, and spinal X-ray abnormal. Incidences of back pain, nuclear MRI abnormal, and spinal X-ray abnormal were high in each of the SI-6603 groups compared to the placebo group, with the latter treatment-related AE occurring most frequently in the 5 U dose group. All AEs were classified as mild or moderate by the Investigators. There was no observed increase in the AE incidence of leg and low back pain accompanying the occurrence of AEs relating to stability of the intervertebral disc and surrounding tissues.

No patients were found to have a definitely elevated serum anti-SI-6603 IgE antibody titer. At Week 13, one patient each from the 2.5 U and 5 U dose groups exhibited a definitely elevated serum anti-SI-6603 IgG antibody titer, but neither experienced any AEs characterized by allergy-like symptoms.

Plasma SI-6603 concentration was below the limit of quantification in all patients at all time points (<100  $\mu$ U/mL).

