#### Clinical Study Protocol CONFIDENTIAL

Adverse event	SI-6603 Group (N=269)					Placebo Group (N=128)			
SOC/PT	AE Subjects (%)		Drug related AE Subjects (%)		AE Subjects (%)		Drug related AE Subjects (%)		
Nuclear magnetic resonance imaging abnormal	69	(25.7)	60	(22.3)	16	(12.5)	10	(7.8)	
Spinal X-ray abnormal	52	(19.3)	38	(14.1)	10	(7.8)	3	(2.3	
Blood triglycerides increased	11	(4.1)	2	(0.7)	5	(3.9)			
Neutrophil count decreased	10	(3.7)	6	(2.2)	8	(6.3)	7	(5.5	
Gamma-glutamyltransferase increased	10	(3.7)			1	(0.8)			
C-reactive protein increased	9	(3.3)	3	(1.1)	2	(1.6)	1	(0.8	
Alanine aminotransferase increased	8	(3.0)	1	(0.4)					
White blood cell count decreased	5	(1.9)	2	(0.7)	3	(2.3)	3	(2.3	
Aspartate aminotransferase increased	4	(1.5)	1	(0.4)					
Blood uric acid increased	4	(1.5)			1	(0.8)			
Blood bilirubin increased	3	(1.1)	1	(0.4)	1	(0.8)	1	(0.8	
Protein total increased	2	(0.7)							
White blood cell count increased	2	(0.7)			1	(0.8)	1	(0.8	
Lasegue's test positive	2	(0.7)	1	(0.4)					
Blood glucose increased	1	(0.4)							
Eosinophil count increased	1	(0.4)	1	(0.4)	1	(0.8)	1	(0.8	
Body temperature increased	1	(0.4)				 			
Platelet count decreased	1	(0.4)	1	(0.4)					
Weight increased	1	(0.4)							
Band neutrophil count increased	1	(0.4)							
Blood pressure increased	1	(0.4)			1	(0.8)			
Blood pressure systolic increased	1	(0.4)				 			
Liver function test abnormal	1	(0.4)			1	(0.8)			
Lymphocyte count increased	1	(0.4)				 			
Blood creatinine increased		 			1	(0.8)	1	(0.8	
Blood pressure diastolic increased					1	(0.8)			
Glucose urine present					1	(0.8)			
Neutrophil count increased					1	(0.8)	1	(0.8	
njury, poisoning and procedural complications									
Ligament sprain	2	(0.7)			1	(0.8)			
Foot fracture	1	(0.4)							
Contusion	1	(0.4)			1	(0.8)			
Bone contusion	1	(0.4)				 			
Muscle strain	1	(0.4)			1	(0.8)			
Animal bite		 			2	(1.6)			
Wound					1	(0.8)			
Arthropod sting					1	(0.8)			
Spinal compression fracture					1	(0.8)			

AE: Adverse event, SOC: System organ class, PT: Preferred term, N: number of patient

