# 9.10 Premature Termination of the Study

If the Investigator, the Sponsor, or the Medical Monitor becomes aware of conditions or events that suggest a possible hazard to patients if the study continues, the study may be terminated after appropriate consultation between the relevant parties. The study may also be terminated early at the Sponsor's discretion in the absence of such a finding.

Conditions that may warrant termination of the study include, but are not limited to:

- The discovery of an unexpected, significant, or unacceptable risk to the patients enrolled in the study (e.g., AE other than those listed in Table 1)
- The occurrence of an AE, as noted below:
  - a. Significant neurologic deficit; for example, progressive weakness or sudden loss of muscle strength, bowel or bladder dysfunction, or other signs and symptoms of cauda equine / conus medullaris involvement, or
  - b. Abnormal X-ray findings of instability, defined as vertebral body angle formed by flexion of  $\geq 5^{\circ}$  or vertebral body translation of  $\geq 3 \text{ mm}$
  - c. Abnormal X-ray or MRI findings which patients exhibit correlating clinical symptoms posing safety concerns, leading the Investigator to judge it necessary for the patient to have surgical intervention

At time of occurrence of these treatment-related AEs, the Sponsor will notify the DSMB and provide the necessary information. DSMB chairperson will determine to make one of two decisions - (1) Continue the study as planned or (2) Request an ad hoc meeting. The Sponsor will judge discontinuation of the study based on the recommendation of the DSMB. The details of the DSMB procedure will be provided in the DSMB charter.

- Failure to enroll patients at an acceptable rate
- A decision on the part of the Sponsor to suspend or discontinue development of the drug

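### Section 1.3.1.4 says without exception that no pain accompanied instability, yet the Phase III summary reports a back-pain AE trend, and Sections 8.6.5 to 8.6.7 relate X-ray findings to VAS only

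*Combined protocol and SAP*

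**What the plan says.** **Risk section.** Section 1.3.1.4 covers past SI-6603 studies, with 269 treated patients as its denominator. It reports treatment-related spinal X-ray abnormalities in 38 of them (14.1%), including 34 events of disc-height decrease and 7 of posterior angle. It then says that "there was no leg pain or back pain accompanying the occurrence of instability of the intervertebral disc and surrounding tissues". Its last sentence adds that "there is a possibility of vertebral body instability (intervertebral posterior angle and vertebral body translation") may occur.

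**Study summaries.** Three of them bear on the same question:

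- Phase I/II follow-up (Section 1.1.2.3; 10 of the 18 patients, retrospective): "In patients who had changes in imaging findings, no clinical symptoms accompanied the changes".
- Phase II/III (Section 1.1.2.5): "There was no observed increase in the AE incidence of leg and low back pain accompanying the occurrence of AEs relating to stability" of the disc and surrounding tissues.
- Phase III (Section 1.1.2.7): 1.25 U patients with stability AEs, given there as disc-height decrease of at least 30% and posterior angle of at least 5°, "showed a trend towards a high incidence of the treatment-related AE of low back pain".

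**Analysis plan.** Sections 8.6.5, 8.6.6 and 8.6.7 each plan an association of the X-ray finding with leg-pain or back-pain VAS. Sections 8.6.8 and 8.6.9 plan two displays for Modic and Pfirrmann changes: a cross-tabulation with leg- and back-pain AEs, and VAS change by group.

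**The concern.** Safety is the primary objective, and whether structural change in the disc is clinically silent is part of it. A reader of the risk section would conclude that no past study linked pain to instability. The Phase III summary in the same protocol does not support that.

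The planned analyses would leave the question open. The trend was reported in AEs. Under Section 6.1.7 a pain AE rests on the investigator's judgment that pain is clinically aggravated, and under Section 6.1.1.4 AEs are recorded continuously. VAS covers the past 24 hours and after treatment is taken only at Weeks 1, 6, 13 and 26 and on discontinuation. Sections 3.3 and 5.7.1 do not restrict medication for the herniation, so a visit VAS may be lowered by treatment while the AE stays on record. A VAS association is useful, but it cannot confirm or remove a trend seen in AEs.

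**Working it through.** **1. Does the risk statement cover the Phase III study?** The pooled figure reproduces: 38/269 = 14.1%. Phase III arm sizes follow from other totals. Section 1.3.1.2 gives 229 patients in the two later Japanese studies and Section 1.1.2.5 gives 147 on SI-6603 in Phase II/III, so 229 − 147 = 82. Placebo: 128 in Table 1, less 194 − 147 = 47, leaves 81. The sum 82 + 81 = 163 matches Section 1.1.2.7. The Phase III rates of 23.2% and 24.4% are then 19/82 with treatment-related X-ray findings and 20/82 with treatment-related back pain. If Table 1 counts patients as that summary does, Phase III supplies 19 of the pooled 38.

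**2. Do the statements conflict?**

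| Source | What it supports |
|---|---|
| Phase I/II follow-up | No symptoms with imaging changes (10 patients) |
| Phase II/III | No observed increase in pain AEs, which is weaker than no pain |
| Phase III | Trend to more treatment-related low back pain, untested |
| Section 1.3.1.4 | No leg or back pain, without exception |

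Only the first row supports wording as strong as the last.

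**3. Does the meaning of instability matter?** The last sentence of Section 1.3.1.4 means angle and translation. So does Section 9.10: "Abnormal X-ray findings of instability, defined as vertebral body angle formed by flexion of" at least 5°, or translation of at least 3 mm. The Phase III summary counts disc height and angle under stability. Angle is common to both, so the statements overlap on either meaning. If the Phase III wording lists two separate findings, however, the trend could come mainly from disc height. The documents do not say.

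**4. How plausible is a literal reading of no back pain?** This applies only if disc height counts as instability. If X-ray findings and back pain were independent in Phase III, the expected overlap is 19 × 20 / 82 = 4.6 patients. The hypergeometric chance of no overlap is C(62,19)/C(82,19) = 0.2%. The actual overlap is not given, and both AEs in one patient need not coincide in time.

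**5. What precision would an AE comparison have?** Half-width = 1.96 × √[p(1−p)(1/n₁ + 1/n₂)], with n₁ + n₂ = 1000 and both groups at the same back-pain rate p.

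- Rates. "Treatment-related AEs of back pain were the highest reported incidence in past studies (64/269 patients") gives p = 64/269 = 23.8%. All-cause back pain in Table 1 gives p = 95/269 = 35.3%.
- Share with disc-height decrease. If the 38 patients had only the two named findings, each counted once per patient, between 38 − 7 = 31 and 34 had it: 11.5% to 12.6%, or 115 to 126 per 1000.
- Share with an angle finding. On the same footing, 38 − 34 = 4 to 7 patients: 1.5% to 2.6%, or 15 to 26 per 1000.

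| Patients with the finding (n₁) | p = 23.8% | p = 35.3% |
|---|---|---|
| Disc height, 126 | ±8.0 | ±8.9 |
| Disc height, 115 | ±8.3 | ±9.3 |
| Disc height, 60 (assumed, about half) | ±11.1 | ±12.5 |
| Angle, 26 | ±16.6 | ±18.6 |
| Angle, 15 | ±21.7 | ±24.4 |

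As an upper bound on the share, Table 1 lists "Spinal X-ray abnormal" of any kind and any cause in 52/269 = 19.3%. If all 52 were disc-height decreases (n₁ = 193), the half-widths would be ±6.7 and ±7.5.

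**The case against.** **The conflict is soft.** Phase III reports a trend without counts, test or interval, and the protocol states it openly. Section 1.3.1.3 also attributes early back pain to degradation of the nucleus and to the injected volume, so overlap within a patient need not mean that pain accompanied the structural change. This stands. It limits the point to the absolute wording.

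**The VAS analyses already address pain.** VAS is patient-reported and scheduled. Pain AEs in an open-label study are open to reporting bias, because investigators may know the image result. This is a good reason to keep VAS and to read the AE tables beside it. It does not explain why the AE table is planned for MRI changes but not for the X-ray findings, for which the only pain trend is reported.

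**The SAP may add the table.** Section 8 leaves detailed methods to a SAP finalised before database lock, and no separate SAP text is in the document. The gap can therefore be shown only for the protocol's outline.

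**Readings that go too far.** A reader might infer that Phase III showed structural change to cause back pain; an untested trend does not show that. A reader might keep the absolute sentence for Phase II/III; that study reported no increase in pain AEs, not an absence of pain. A reader might extend the conflict to leg pain or to the separate sentence on Modic changes; the Phase III trend concerns neither.

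**Conclusion.** The point holds in limited form. The no-pain sentence in Section 1.3.1.4 is stronger than the protocol's own summaries allow: it does not fit the Phase III back-pain trend and overstates the Phase II/III result. The protocol's outline would not examine that trend on the measure in which it was reported.

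The weight is moderate: no endpoint, population or procedure changes. A back-pain comparison by disc height could be estimated to about ±8 to ±9 points. That assumes about 12% of 1000 patients have the finding, a share taken from treatment-related events pooled over doses of 0.5 to 10 U and up to one year. The true share at 26 weeks may differ, and a lower one widens the interval. Angle, at about ±17 to ±24 points, is descriptive only. No translation count is given.

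Two cut-offs affect the groups. Section 8.6.5 counts disc-height changes of at most 30%, whereas Sections 6.1.1.2 and 6.1.3.1 define the AE as a decrease of at least 30%. Read literally, Section 8.6.5 gives the wrong percentage. For the angle, Section 6.1.3.2 uses at most −5° for the eCRF entry and at least 5° for the AE. A reader might call that an error too, but it may be a sign convention, and the measurement figure is not shown.

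**What to change.** 1. In Section 1.3.1.4, replace the absolute sentence with the result of each study as its own summary gives it (Sections 1.1.2.3, 1.1.2.5 and 1.1.2.7). State whether instability includes disc-height decrease.
2. Reconcile the disc-height cut-off in Section 8.6.5 with Sections 6.1.1.2 and 6.1.3.1, because it defines the groups. Confirm the sign convention for the angle in Section 6.1.3.2.
3. In Sections 8.6.5 to 8.6.7, and in the SAP before database lock, add the cross-tabulation already planned in Sections 8.6.8 and 8.6.9. Set patients with and without each finding (disc-height decrease of at least 30%, angle finding, translation of at least 3 mm) against treatment-emergent leg- and back-pain AEs, all and treatment-related.
4. Give a risk difference with 95% CI only for back pain by disc height, and leave the rest descriptive. Keep the VAS associations.

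**Cost.** A short background edit, and 3 findings × 2 pain sites × 2 (all, related) = 12 exploratory comparisons, 2 of them with an interval. No new data are needed. The comparisons are not randomised and are open to reporting bias, so they must be read beside the VAS results. Imaging after treatment is first scheduled at Week 6, so AE onset dates cannot show whether pain followed the structural change. The risk statement becomes slightly less favourable.
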